5.4. SUBJECT COMPLIANCE

Compliance Log. Subjects will be asked to complete a Silverlon® Compliance Log to document the removal and application of the Silverlon® dressing during the course of the study. They will enter the date and time of removal and application of the Silverlon® dressing every time these actions occur. This will provide insight into how many hours per day the Silverlon® dressing was worn on the irradiated breast. Additionally, study personnel will ask the subject if they have been "wearing the Silverlon® while sleeping" each week by phone and at each study visit.

5.5. COST TO SUBJECTS

There are no costs for participation for research subjects in this study. Silverlon® dressings will be provided to the subjects at no cost. There is no additional travel above the usual travel required for the course of radiation therapy associated with this study.

5.6. REIMBURSEMENT FOR PARTICIPATION

All subjects will be reimbursed \$200.00 for completion of all study procedures in this study. Payment will be prorated based on the number of study visits completed in the study. Subjects will be paid \$20 for completion of baseline visit (Pre-Radiation visit), \$60 for completion of Mid-Study Visit, \$60 for completion of Completion of RT Visit, and \$60 for completion of 2-Week Post-RT Visit. A check or VISA Gift Card will be issued and mailed to the subject after completion of the 2-Week Post-RT Visit or at their completion of study participation.

6. CONCOMITANT AND DISALLOWED MEDICATIONS

This is a safety study for Silverlon® dressing to discern FDA indication for radiation dermatitis. For this reason, current standard of care for radiation dermatitis will not be allowed during the study. Topical agents usually provided to patients during radiation therapy, such as RadiaPlex, Aquaphor, or other moisturizing lotions are not permitted during the study. The goal of the study is to determine if Silverlon® dressing is safe to use during radiation therapy and can be used in place of other current topical agents. Oral antihistamines are permitted to help with itching or other symptoms. Standard of care for radiation dermatitis is only permitted if the subject is withdrawn from the study due to the progression of the skin reaction to RTOG score ≥ 3 (i.e., moist desquamation in areas that are not skin folds). If the subject is withdrawn for this reason, then standard of care (i.e., silver sulfadiazine, topical steroids, Mepilex, etc.) are permitted.

6.1 USE OF TOPICAL AGENTS FOR WORSENING SKIN REACTIONS

In an effort to prevent moist desquamation and reduce patient withdrawal from study, use of standard of care topical medications may be allowed only under the following circumstances:

• Subject should have documented worsening skin reaction that requires additional treatment per the treating physician, and be ordered/prescribed the topical agent by the

Page 27 of 41 RSRB STUDY00004587 Version Date: 09/14/2021 NCT04238728

- treating provider on study.
- The type, dose and frequency of the medication prescribed will be documented in the subject's study and medical record.
- The subject will be instructed to remove the Silverlon® dressing before applying the topical agent, and reapply the dressing approximately one (1) hour after application of the topical agent to allow for absorption into the skin. The subject will be asked to document the removal and re-application of the dressing in their Subject Compliance Log.

7. SUBJECT WITHDRAWALS

Subjects will be advised during the consent process that they have the right to withdraw from the study at any time without prejudice or reason. Subjects that withdraw from the study will be replaced with another subject. Subjects will continue to receive radiation therapy as prescribed with standard of care with their treating radiation oncologist. The reason for discontinuation will be recorded in the subject's medical records. The date of occurrence and reasons for any subject withdrawal will be recorded and documented on the **Withdrawal Form**.

Subjects can be withdrawn from the study by the investigator or radiation oncologist for: non-compliance to study procedures; termination of funding; allergic reaction to Silverlon® dressing; worsening of the disease under study; intercurrent illness; pregnancy; or progression of skin reaction to RTOG score ≥3 in the radiation area where the Silverlon® dressing has been applied (i.e., whole breast). RTOG score ≥3 requires patients to have areas moist desquamation outside of skin fold regions (i.e., which would exclude inframammary fold and axillas because these are skin fold regions). Additionally, an area of moist desquamation that is >50% of the radiation treatment area (i.e., RISRAS-HPA score ≥3). Therefore, a large area of moist desquamation outside of skin folds would suggest withdrawal. Pinpoint areas and fold areas of moist desquamation could not require withdrawal. Patients withdrawn from the study will stop using Silverlon® dressing, but continue to receive radiation therapy on their normal schedule as prescribed by the treating radiation oncologist. For patients withdrawn from the study, standard of care for radiation dermatitis will be provided by the treating radiation oncologist, who will continue to follow the patient as per their normal clinical routine. The date of occurrence and reasons for any subject withdrawal will be recorded and documented on the Withdrawal Form. An adverse event will be reported if the skin reaction is RTOG ≥4. This grade of radiation dermatitis is severe and should be reported on the AE Source Doc and following reporting procedures stated in §10. Allergic reaction to Silverlon® dressing will be reported as an unexpected side effect on the AE Source Doc.

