8. EARLY STOPPING PROCEDURES

The study will be stopped if we observe a significantly increased rate of confluent moist desquamation (i.e., RTOG \geq 3; large areas (>50% of radiation treatment area) of moist desquamation outside of skin folds) in subjects using the Silverlon® dressing. The study will be stopped if 6/15 or fewer subjects who initiated treatment with Silverlon® dressing are withdrawn due to RTOG score \geq 3. This result would suggest a two-fold increase in the rate of confluent moist desquamation with patients using Silverlon® dressing. If the first 6 subjects are withdrawn due to RTOG score \geq 3 while using the dressing (i.e., 6/6), the study will be stopped due to the significantly increased rate of confluent moist desquamation. If the study is stopped early, participant reimbursement will be issued to any subjects remaining on study.

Page 28 of 41 RSRB STUDY00004587 Version Date: 09/14/2021 NCT04238728

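### The stopping event is labelled RTOG ≥3 but described with a >50% area threshold that the trial's RTOG scale lacks, so some grade 3 reactions may go uncounted

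*Combined protocol and SAP*

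**What the plan says.** Four sections of the combined protocol and SAP bear on the event.

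- **Section 5.3 (RTOG scale).** Grade 3 is confluent moist desquamation outside skin folds, or pitting edema. Patchy moist desquamation is grade 2. No percentage of the field appears. Percentage of area belongs to a different instrument in the same section, the RISRAS healthcare professional scale (RISRAS-HPA), where moist desquamation over >50–75% of the area scores 3.
- **Section 6.** RTOG ≥3 is explained as "i.e., moist desquamation in areas that are not skin folds".
- **Section 7.** The base statement is "RTOG score ≥3 requires patients to have areas moist desquamation outside of skin fold regions". Next comes the fragment "Additionally, an area of moist desquamation that is >50% of the radiation treatment area", tied to a RISRAS-HPA score of 3 or more. The section concludes: "Therefore, a large area of moist desquamation outside of skin folds would suggest withdrawal". It also says: "Pinpoint areas and fold areas of moist desquamation could not require withdrawal".
- **Section 8.** The event is RTOG ≥3, explained as "large areas (>50% of radiation treatment area) of moist desquamation outside of skin folds". The study stops if "6/15 or fewer subjects who initiated treatment with Silverlon® dressing are withdrawn due to RTOG score" of 3 or more, or if the first six subjects are all withdrawn for that reason. The justification is: "This result would suggest a two-fold increase in the rate of confluent moist desquamation with patients using Silverlon® dressing".

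Section 11 makes withdrawal mandatory for dermatitis of RTOG grade 4 or above, or for another adverse reaction of grade 3 or higher where the dressing is applied. It does not clearly settle what happens to grade 3 dermatitis.

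**The concern.** A stopping rule needs an event that two investigators would count in the same way. Here the triggers count withdrawals, and withdrawal for a grade 3 skin reaction rests on section 7, where it is discretionary and the area condition is grammatically incomplete. The scale used to grade the reaction has no area condition; the section 8 explanation of the same grade does. A subject can therefore be grade 3 on the trial's own scale and fall outside the event described for stopping.

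These are the protocol's only numeric stopping triggers, although monthly and continuous safety review run beside them. If the counted event is narrower than the label suggests, confluent grade 3 reactions over less than half the field can accumulate without moving the count. The two-fold justification cannot be checked either, because no reference rate is given for the broad event or the narrow one.

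**Working it through.** **1. The same subject under each section.** Take a hypothetical subject with confluent moist desquamation outside the folds over 30% of the field.

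| Section | Is this the event? |
|---|---|
| 5.3, RTOG | Yes: grade 3, no area condition |
| 5.3, RISRAS-HPA | Moist desquamation score 2 (>25–50%), so below 3 |
| 6 | Yes: outside the folds, no area condition |
| 7, if both elements are required | No: area not above 50% |
| 7, if either element suffices | Yes |
| 8, explanation of the event | No: area not above 50% |
| 8, trigger sentences | Only if the subject was withdrawn, which returns to section 7 |

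Section 7 addresses large areas at one end and pinpoint or fold areas at the other. The band between, where this subject lies, is not assigned. Section 6 is also broader than 5.3, because it drops the requirement that the desquamation be confluent. Pitting edema, a grade 3 finding in 5.3, is not mentioned in 6, 7 or 8; that is a minor point.

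**2. The plan's own figure.** I read the first trigger as six withdrawals among fifteen or fewer treated subjects. Then 6/15 = 0.40, and two-fold implies a reference rate of 0.40 / 2 = 0.20. The documents give no 20% rate for either event. Section 1.2 gives 30–40% for moist desquamation in unselected breast patients and 38% in the cited breast study of this type of dressing. Neither figure is restricted to confluent non-fold grade 3, and neither refers to >50% of the field, so neither can serve as the reference. The two-fold statement can be neither reproduced nor refuted.

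**3. Sensitivity of the trigger to the event counted.** Every event rate here is an assumption. The chance of reaching six within fifteen subjects is P(X ≥ 6) = Σ C(15,k) p^k (1−p)^(15−k), summed over k = 6 to 15. The chance that the first six are all withdrawn is p^6, which is one way of meeting the first trigger.

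| Assumed rate p | P(X ≥ 6 of 15) | p^6 |
|---|---|---|
| 0.10 | 0.002 | 0.000001 |
| 0.20 | 0.061 | 0.00006 |
| 0.30 | 0.278 | 0.0007 |
| 0.40 | 0.597 | 0.004 |

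If the area threshold excluded half of RTOG ≥3 events (an assumed share), a rate of 0.40 would become 0.40 × 0.5 = 0.20, and the stopping probability would go from 0.597 to 0.061. From 0.20 to 0.10 it would go from 0.061 to 0.002. The documents give neither the rate nor the share, so these rows show how the rule behaves and do not estimate its performance in this trial.

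**The case against.** The strongest reply is that sections 7 and 8 are the operative ones and fit a single reading. Section 7 moves from non-fold desquamation, through the added >50% condition, to a conclusion about large areas; section 8 states both elements together. Requiring either element alone is a weak reading, because desquamation over half a whole-breast field would nearly always extend beyond the folds. Section 5.3 is a grading scale for an exploratory outcome and section 6 is a medication rule. Withdrawing subjects only at a more extensive lesion is a legitimate choice, and some clinical discretion is plainly intended.

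Most of this stands: the text does favour requiring both elements. It does not remove the contradiction, because the event is still called RTOG ≥3, the trigger sentences carry only that label, and the trial's RTOG scale does not contain the threshold.

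It also stands that the primary outcome, dressing-related adverse events, is not redefined by this, although a withdrawal does take a subject out of the fully evaluable set. Weekly examinations, visit photographs, recorded withdrawal reasons and monthly review would allow partial reconstruction. Percent area could still be missing for a withdrawal between visits: RISRAS-HPA is scheduled only at the Mid-Study, EndRT and 2-Week Post-RT visits, and the Withdrawal Form is described as holding time and reasons.

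A reader might go further and infer that the rule is miscalibrated, or that the threshold cuts the chance of stopping by some stated amount. The documents do not support that. They give no rate for either event, and if the intended reference rate belongs to the >50% event, event and benchmark match. That 5/15 and 6/15 lead to different decisions is true of any threshold rule; it matters here only because the text lets the same subject fall on either side.

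**Conclusion.** The point holds as an inconsistency in the definition of the event behind the stopping triggers. RTOG ≥3 has no area threshold in 5.3 and 6, an unsettled one in 7 and an explicit one in 8, while both triggers depend on withdrawals for RTOG ≥3. Sections 7 and 8 together lean towards requiring more than half the field, in which case confluent non-fold reactions over a smaller area are grade 3 on the trial's scale and may go uncounted.

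One subject classified differently is enough to change the decision at the boundary; that needs no assumed rate. The effect on the stopping probability cannot be sized from the documents, and no mismatch with the intended reference rate is shown. The implied 20% rests on reading the trigger as 6/15 = 40% and taking two-fold literally. This should be fixed: it concerns safety monitoring and the repair is cheap, but it does not undermine the primary analysis.

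**What to change.** Use one event in sections 6, 7 and 8, and make the trigger count that event. Either choice is defensible.

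- **(a) Broad event.** Count every treated subject who reaches RTOG ≥3 on the 5.3 scale, whether or not withdrawn. Record the RTOG grade at the weekly examination already held, and delete the >50% condition from section 8. Counting subjects who are not withdrawn is essential: if the trigger still counted withdrawals and withdrawals still followed >50%, the count would stay tied to the narrow event.
- **(b) Narrow event.** If >50% is intended, name the event as RTOG ≥3 plus a RISRAS-HPA moist desquamation score of 3 or more, and stop calling it RTOG ≥3 alone.

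In both cases, complete the section 7 sentence so that the role of >50% is explicit. State the reference rate for the chosen event beside 6/15, and recheck the boundary if that rate is not about 20%. Record the RTOG grade and the RISRAS-HPA moist desquamation score at any visit leading to a skin-reaction withdrawal.

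The cost is wording in three sections and two score fields at withdrawal; option (a) adds one RTOG field at the weekly examination. Option (a) also brings a somewhat higher chance of stopping, which is why the reference rate must belong to the event chosen.

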8. EARLY STOPPING PROCEDURES

The study will be stopped if we observe a significantly increased rate of confluent moist desquamation (i.e., RTOG \geq 3; large areas (>50% of radiation treatment area) of moist desquamation outside of skin folds) in subjects using the Silverlon® dressing. The study will be stopped if 6/15 or fewer subjects who initiated treatment with Silverlon® dressing are withdrawn due to RTOG score \geq 3. This result would suggest a two-fold increase in the rate of confluent moist desquamation with patients using Silverlon® dressing. If the first 6 subjects are withdrawn due to RTOG score \geq 3 while using the dressing (i.e., 6/6), the study will be stopped due to the significantly increased rate of confluent moist desquamation. If the study is stopped early, participant reimbursement will be issued to any subjects remaining on study.

Page 28 of 41 RSRB STUDY00004587 Version Date: 09/14/2021 NCT04238728

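### Section 8's numerical stopping limit is ambiguously worded and counts discretionary withdrawals rather than the skin event it is meant to watch

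*Combined protocol and SAP*

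**What the plan says.** Section 8 opens with a qualitative rule: the study stops if "we observe a significantly increased rate of confluent moist desquamation", which it describes as RTOG 3 or more with "large areas (>50% of radiation treatment area) of moist desquamation outside of skin folds". It then gives a number: "The study will be stopped if 6/15 or fewer subjects who initiated treatment with Silverlon® dressing are withdrawn" because of an RTOG score of 3 or more. Of that count it says: "This result would suggest a two-fold increase in the rate of confluent moist desquamation with patients using Silverlon® dressing". A further sentence covers the extreme case: "If the first 6 subjects are withdrawn due to RTOG score" of 3 or more, that is 6 of 6, the study also stops. No reference rate, significance level or test is given.

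Four other places bear on what is counted:

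- **Section 7** is permissive: "Subjects can be withdrawn from the study by the investigator or radiation oncologist for" a list of reasons that includes progression to RTOG 3 or more. It carries the same area condition as Section 8 (more than 50% of the treated area, equated with a RISRAS professional score of 3 or more). It treats a large area outside skin folds as pointing towards withdrawal.
- **Section 11** makes withdrawal mandatory only for dermatitis of RTOG 4 or above, or for another reaction of grade 3 or higher in the dressed area.
- **Section 6** says: "Standard of care for radiation dermatitis is only permitted if the subject is withdrawn from the study due to the progression of the skin reaction". The grade it names is RTOG 3 or more, which it explains as "moist desquamation in areas that are not skin folds", with no area threshold.
- **The RTOG scale in Section 5.3** defines grade 3 without an area threshold.

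**The concern.** Safety is the primary objective, and this is the only place where the plan attaches a number to stopping. The 6-of-6 sentence is a special case of the same limit when the limit is read as intended. Three things weaken it.

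1. Taken by itself, the operative sentence can be read in the wrong direction.
2. It counts a management decision (withdrawal) where the rule's purpose is to watch a clinical event. If the two differ, the count can only fall short of the number of events.
3. The two-fold benchmark has no stated base, so nobody can check how often the limit would stop the study needlessly or fail to stop it when it should.

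**Working it through.** **Inputs.** Limit of 6, denominator 15, and the two-fold remark (Section 8). Permissive withdrawal (Section 7). Mandatory withdrawal from RTOG 4 or for other reactions of grade 3 or higher (Section 11).

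**Step 1: the plan's own figure.** 6/15 = 0.40, and a doubling implies a reference of 0.40 / 2 = 0.20. The two-fold statement cannot be reproduced from the documents, because none gives a breast-patient rate for RTOG 3 or more. The planning figure of 20% in Sections 3.1, 3.9 and 13.1 is overall withdrawal, a different quantity. Section 1.2 gives 30–40%, and 38% in the cited breast trial, but for any moist desquamation. Against 30%, 38% and 40%, 6/15 is a ratio of 1.33, 1.05 and 1.00. These ratios do not settle the rate for the narrower event.

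**Step 2: the two readings.** Let X be the number counted among the first 15 treated subjects.

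- If *or fewer* qualifies the whole fraction, the study stops when X ≤ 6. That has probability 0.982 at a true 20% and 0.610 at a true 40%, and zero withdrawals would trigger it.
- If *or fewer* qualifies the 15, the study stops once 6 withdrawals occur among 15 or fewer subjects. Because the count never falls, this is the same as X ≥ 6 of 15.

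Only the second reading fits a limit meant to show a doubling, and only under it is 6 of 6 a natural special case.

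**Step 3: operating characteristics of the intended reading.** P(X ≥ 6) = 1 − Σ C(15,k) p^k (1−p)^(15−k), summed over k = 0 to 5, with every event counted.

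- p = 0.20: 0.0611, the false-stop probability at the implied reference.
- p = 0.40: 0.5968, so a true doubling is missed with probability 1 − 0.5968 = 0.4032.

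These figures leave out the qualitative sentence, which could also stop the study.

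**Step 4: effect of counting withdrawals.** Suppose one subject among the first 15 has the event but is kept on study. Seven events (7/15 = 47%) are then needed to produce six withdrawals.

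| True event rate | All events counted, P(X ≥ 6) | One event uncounted, P(X ≥ 7) |
|---|---|---|
| 20% | 6.1% | 1.8% |
| 40% | 59.7% | 39.0% |

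Alternatively, suppose a fixed share of qualifying subjects is withdrawn and the true rate is 40%. With 75% withdrawn the counted rate is 0.40 × 0.75 = 0.30, and the chance of reaching the limit is 27.8%. With 50% withdrawn it is 0.40 × 0.50 = 0.20, and the chance is 6.1%. The documents give no retention rate, so all of these are illustrations.

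**Step 5: what the event is.** Sections 7 and 8 attach the area condition. Section 6 and the RTOG scale do not. The four texts therefore do not define one event.

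**The case against.** The strongest reply has four parts.

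- **Direction.** A reader might infer that the limit is simply backwards. The documents do not support that: 6 withdrawals among 15 or fewer treated subjects is an ordinary reading of the sentence, and the only one consistent with the sentences around it. What stands is ambiguity.
- **Size of the undercount.** A reader might infer that every RTOG 3 subject kept on study is an event the limit should have counted. Sections 7 and 8 share the large-area condition, so a subject with limited RTOG 3 is arguably outside what Section 8 watches. The gap mainly concerns large-area cases kept on study. It is narrower, but real, because Section 7 does not oblige withdrawal even for those.
- **Conflict between sections.** Withdrawal that is permitted at RTOG 3 and required at RTOG 4 is coherent, and Section 6 does not say that every RTOG 3 subject is withdrawn. This part of the reply stands. The area condition and the link between event and withdrawal still need reconciling.
- **Other safeguards.** Section 8's first sentence does not depend on withdrawal and has no subject cut-off. Section 9.2 provides continuous review, and Section 11 provides monthly review and weekly skin examination. These could catch an unwithdrawn case, but by judgement and outside the numerical limit. They are also why the lack of a number after subject 15 should not be called an error.

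A reader might also call 6/15 an error because its one-sided exact p against 20% is 0.061. With no significance level stated there is nothing for it to violate. The missing level and test are a documentation gap.

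**Conclusion.** The point holds in this form: the sentence is ambiguous, though its intent can be recovered, and the limit counts discretionary withdrawals where Section 8 watches an observed event rate. A subject with the qualifying event who stays on study is left out of the numerical limit. Only the qualitative sentence and the ongoing reviews would catch her.

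If one such subject is assumed, the chance of reaching the limit at a true 40% falls from 59.7% to 39.0%. The actual loss is unknown, because the documents do not say how often such subjects would be kept on. The unstated 20% reference is a supporting point. It is inferred from 6/15 and the two-fold remark, and the 6.1% and 40.3% figures depend on it. All probabilities assume independent subjects with a common event rate. The matter should be fixed because it concerns a safety decision threshold and the correction is short.

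**What to change.** (a) If that is the intent, reword the limit as: 6 or more subjects with the event among the first 15 or fewer who started the dressing.

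(b) Define the counted event once, stating whether the 50% area condition applies. Reconcile Sections 5.3 (RTOG scale), 6, 7, 8 and 11 on that definition and on withdrawal. Count every subject recorded with the event, whether or not she is withdrawn. This changes only the count, not who is withdrawn or how anyone is treated. Counting every RTOG 3 or higher score against an unchanged 6/15 without first settling the definition could broaden the event beyond what Sections 7 and 8 describe.

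(c) State the reference rate for that same event with the resulting operating characteristics (at 20%, 6.1% false stops; at 40%, 40.3% misses), or delete the significance and two-fold claims.

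The cost is a short amendment with no new visits. RTOG and RISRAS are already rated at the Mid-Study, EndRT and 2-Week Post-RT visits. The weekly form in Section 5.3 has no RTOG grade field, so one could be added if events between rated visits are to be graded systematically; that is a little extra data entry. The downside is somewhat more stops. Where one event would otherwise go uncounted, the stop probability rises from 1.8% to 6.1% at a true 20%, alongside the gain from 39.0% to 59.7% at a true 40%.
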